4. RATIONALE FOR CURRENT STUDY

If selenium supplementation were effective in reducing bone turnover and increasing BMD, this would offer an affordable, low risk prevention strategy that could be attractive to patients because it is a nutritional supplement, rather than a 'medicine'.

This study will give clear evidence of efficacy, and if positive, will identify the likely effective dose.

If this study is positive, we will immediately apply for funding to take the best dose (the lowest dose with a clinically significant clinical effect on bone turnover) into a longer study with bone density as the primary endpoint.

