8. PLANNED INTERVENTIONS

The intervention is a medicinal product containing sodium selenite. We will study two doses: 50 and 200mcg daily. The preparation is sodium selenite tablets 'Selenase' 50mcg and 200mcg (Biosyn, Germany). The tablets will be overencapsulated and a matching placebo will be manufactured to maintain the blind.

The mean difference between selenium levels in a replete population (USA) and the UK is about 60mcg/L. The mean increase in serum selenium with 200mcg/day is 90 mcg/L (19). 200mcg/day is a clinically effective dose in Graves' ophthalmopathy. Therefore 200mcg will be enough to achieve repletion in the majority of subjects and to determine whether selenium repletion has a clinically significant effect on bone turnover. If we see no effect at this dose we will be confident to accept the null hypothesis.

The 50mcg dose will assess whether a lower dose might be effective for musculoskeletal health – if its effect on bone turnover is similar to the 200mcg dose we could recommend the 50mcg dose for clinical use, at lower cost and lower risk of adverse effects.

This is a short, low risk study of a medication that we expect to be well tolerated. We are very experienced in recruiting and retaining patients in clinical trials. We expect compliance to be good and loss to follow-up to be low (less than 10%). We will make telephone contact with participants between study visits (every month) to maintain their engagement and check for adverse effects.

The required minimum sample size for the primary endpoint is 21 per group. We will recruit 33 per group into the primary analysis to allow for drop-out, group imbalance and secondary endpoint analysis.

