13. STATISTICS

13.1 Power calculation

A 20% (10nmol BCE/mmolCr) decrease in urine NTX is a plausible and clinically significant effect size.

In a previous study, 200mcg daily for six months increased serum selenium by 90mcg/L (19).

In our observational study of serum selenium and bone turnover markers, the regression coefficient of serum selenium and NTX/Cr was -0.101 (9), so if the relationship were causative we would expect an increase in serum selenium of 90mcg/L to be associated with a reduction in urine NTX/Cr of 9 nmol BCE/mmolCr (approximately 20%).

In support of this estimate, we would not expect as large a change in bone turnover as would be seen with a potent anti-resorptive drug such as a bisphosphonate (about 60%), but it might be

similar to a weaker anti-resorptive such as a SERM. In a study of six months' treatment with the SERM lasofoxifene (37), NTX decreased by 29%. We have also used this study as a model for the likely SD (12.5) and the correlation between NTX/Cr at baseline and six months (0.7).

A 20% decrease in NTX is clinically significant; a 20% decrease in NTX (about 1 standard deviation decrease) with bisphosphonate treatment is associated with a 30% decrease in incident vertebral fracture (38).

To achieve 90% power to detect this mean difference at the 2.5% (two-sided) level will require 21 patients per group. To allow for dropout, group imbalance and the secondary endpoint analyses we will recruit 33 patients per group with serum selenium below 120mcg/l (99 patients in total).

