13.2 Analysis plan

A detailed statistical analysis plan (SAP) will be developed and finalised prior to the locking of the trial database in consultation with the trial steering committee.

We will conduct an intention-to-treat analysis (all randomised participants) and per-protocol analysis (completing participants with 75% compliance).

Primary endpoint:

Urine NTX at six months in postmenopausal osteopenic or osteoporotic women with baseline serum selenium below 120 mcg/l

Baseline data will be assessed for comparability between the treatment groups. NTX/Cr will be assessed visually for normality and if it is non-Normal a log-transform will be applied, with results reported as percentage difference between geometric means. Analysis of covariance (ANCOVA) will be used to compare mean NTX/Cr between the groups adjusting for baseline NTX/Cr measurements. The Hochberg procedure will be used to account for multiple comparisons; P-values are ordered from smallest to largest. If the largest P-Value is less than 0.05 then all null hypotheses can be

rejected. If not, if the second P-value is less than 0.05/2, then all bar the largest can be rejected, and so on (SA Julius, An Introduction to Statistics in Early Phase Trials).

Secondary endpoints:

Urine NTX at three months: analysis as described for the primary endpoint

Serum selenium, SePP, serum CTX, PINP, osteocalcin, thyroid function, glucose and insulin at three and six months: analysis as described for the primary endpoint.

BMD by DXA at six months: analysis as described for the primary endpoint.

We will examine impact of baseline selenium levels on the NTX response to selenium supplementation by fitting a linear model with NTX at follow-up as the dependent variable and baseline selenium, baseline NTX and dose as independent variables. With n=66 (receiving active treatment) the minimum correlation that can be detected with 90% power and 5% significance level is 0.44.

Short physical performance battery, grip strength, hydroperoxidases, glutathione peroxidase activity, highly sensitive CRP, IL-6 analysis as described for the primary endpoint.

There is no planned interim analysis of outcome measures. There will be an interim analysis of baseline serum selenium to determine the final sample size.

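### Does the protocol need a definition of a 'similar' effect before the 50 mcg arm can be compared with the 200 mcg arm?

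*Protocol*

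**What the plan says.** Section 8 gives the reason for each dose. The 200 mcg arm is there "to determine whether selenium repletion has a clinically significant effect on bone turnover", followed by "If we see no effect at this dose we will be confident to accept the null hypothesis". The 50 mcg arm is there to see whether a lower dose might work: "if its effect on bone turnover is similar to the 200mcg dose we could recommend the 50mcg dose for clinical use".

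Section 13.1 sizes the trial on a 10 nmol BCE/mmolCr (20%) fall in urine NTX, with SD 12.5 and a baseline to six-month correlation of 0.7: "To achieve 90% power to detect this mean difference at the 2.5% (two-sided) level will require 21 patients per group". Recruitment is set at 33 per group, and section 8 expects loss below 10%.

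Section 13.2 gives the analysis: "Analysis of covariance (ANCOVA) will be used to compare mean NTX/Cr between the groups adjusting for baseline NTX/Cr measurements", with the Hochberg procedure ("if the second P-value is less than 0.05/2, then all bar the largest can be rejected"). It does not list the comparisons in the Hochberg family, and it leaves detail to a SAP to be finalised before database lock.

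Section 4 says what follows a positive result: the smallest dose showing a clinically meaningful effect on bone turnover goes "into a longer study with bone density as the primary endpoint".

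**The concern.** A possible recommendation of the lower dose is tied to a word the protocol does not define. Hochberg says when null hypotheses may be rejected, and failure to reject a 50 versus 200 mcg difference does not show that the doses act alike. With about 30 women per arm, a lower dose that is clearly weaker could still fail to differ significantly from the higher one. If the meaning of similar were picked after unblinding, the same data could support or undercut the lower dose.

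Two smaller points go with this. Section 8 speaks of clinical use where section 4 speaks of a further trial, and the remark about accepting the null hypothesis does not say which effect size would have been excluded.

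**Working it through.** **Inputs (section 13.1 unless noted).** Target 10 nmol; expected effect of 200 mcg about 9 nmol (0.101 × 90); SD 12.5; correlation 0.7; two-sided 2.5%; 90% power; 33 per group; loss under 10% (section 8), so about 30 evaluable.

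**1. The protocol's own figure.** ANCOVA residual SD = 12.5 × √(1 − 0.7²) = 8.93. With n = 2 × 8.93² × (2.241 + 1.282)² / 10², the result is 19.8, so 20 per group; a t-based version gives 22. At 21 per group the noncentral t power for 10 nmol is 89.8%. The stated 21 is reproduced.

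**2. Precision of 50 versus 200 mcg.** SE = 8.93 × √(2/n); half-width = t × SE with 2n − 3 degrees of freedom.

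| n per arm | SE | 95% half-width | share of 10 nmol | share of 9 nmol |
|---|---|---|---|---|
| 30 | 2.30 | 4.6 | 46% | 51% |
| 33 | 2.20 | 4.4 | 44% | 49% |

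The half-width is half the effect only against the 9 nmol expectation. These figures hold on the untransformed scale used for sizing. If NTX is log-transformed, as section 13.2 allows, the interval would be a ratio.

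**3. What this precision can show.** If the two doses are truly equal, the chance that the interval (95% or 97.5%, n = 30 or 33) excludes a given loss is 17–27% for 3 nmol, 37–52% for 4.5, 62–77% for 6 and 77–88% for 7. The protocol gives no margin, so these margins are assumptions, and the answer depends almost wholly on which one is taken.

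**4. How often a weaker 50 mcg dose would be called similar.** Simulation of 400,000 three-arm trials per setting, with the 200 mcg effect at 9 nmol and the 50 mcg effect assumed. All three readings require 200 mcg to beat placebo.

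| Reading | 50 mcg effect 4.5 | 50 mcg effect 2.25 |
|---|---|---|
| doses not significantly different | 46–57% | 13–22% |
| the same, and 50 mcg also beats placebo | 30–33% | 5–6% |
| 50 mcg estimate at least 80% of the 200 mcg estimate | 8–9% | under 1% |

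The wide spread belongs to the 4.5 nmol assumption. If the serum rise is proportional to dose (also an assumption), the 50 mcg rise is 90 × 50/200 = 22.5 mcg/L. The NTX effect is then 22.5 × 0.101 ≈ 2.3 nmol, close to the right-hand column. The dose difference is about 6.75 nmol, which the trial detects with 82–86% power at the 5% level.

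**5. The null hypothesis remark.** If 200 mcg versus placebo is not significant at 5%, the estimate is below one half-width. The 95% limit is then below two half-widths: 2 × 4.39 = 8.8 nmol (n = 33) or 2 × 4.615 = 9.2 nmol (n = 30). On the planning SD, a non-significant result at that level already excludes 10 nmol. At the 2.5% level, with a 97.5% interval, the limit is 2 × 5.05 = 10.1 or 2 × 5.31 = 10.6 nmol, a marginal exception. If the true effect is zero, the interval excludes 10 nmol in 98–99% of trials.

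**6. Sections 4 and 8 side by side.** Section 4 asks whether a dose has a clinically meaningful effect, and section 13.1 attaches 10 nmol to that idea. Section 8 adds that a lower dose doing about as well would be attractive on cost and risk. It says the team could recommend that dose, and gives no time for doing so. Section 4 says which trial comes next. The emphasis differs, but both statements can hold.

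**The case for a change.** The best case for a change is that a SAP can define similarity but cannot buy precision. With 33 per arm fixed in the protocol, observed equality of the two doses leaves a loss of 4.4 to 4.6 nmol open. A sentence pointing towards clinical use should not rest on that, and a few words plus one reported contrast would cure it at no cost in patients.

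The arithmetic stands, and so does the warning that non-significance is not similarity. Two things weaken the step from there to a change.

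- The protocol makes no claim that the arithmetic refutes. It states no power for similarity, no equivalence test, and no rule turning non-rejection into a recommendation.
- The suggested remedy, an interval that excludes a loss beyond a margin fixed before unblinding, leaves that margin blank. It would pass the same open question to the same later document.

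The readings in step 4 also leave out the one selection criterion the protocol states, in section 4. That criterion can be judged against placebo, the kind of comparison the trial is sized for.

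**Conclusion.** No change to the plan is needed. The undefined word sits in a conditional sentence of rationale, and interpretation of the dose contrast is a gap that analysts fill sensibly by reporting the 50 minus 200 mcg estimate with its interval from the ANCOVA already planned. A reader of the results should know that this interval will be about ±4.4 to 4.6 nmol, or 44–46% of the sizing target. It can reveal a large dose difference but will seldom establish close similarity.

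The primary comparison and its sample size are unaffected. Rewording the null hypothesis remark gains almost nothing, because a non-significant result at 5% already excludes 10 nmol. Sections 4 and 8 differ in emphasis without contradicting each other.

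This rests on the planning SD of 12.5 and correlation of 0.7, on 30 to 33 evaluable women per arm, and on an untransformed analysis. The 50 mcg effects, the margins and the 80% reading are assumptions without a source in the protocol. It would be a different matter if a report presented a non-significant 50 versus 200 mcg difference as evidence that the doses are equivalent; nothing in the protocol plans that.

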9. OUTCOME MEASURES

Primary endpoint:

Between-group difference in urinary N-telopeptide of type I collagen (NTX) at six months

Bone turnover markers change much more rapidly than BMD, so we can determine quickly and cost-effectively if selenium is likely to have beneficial effects, and if it is well tolerated and safe in the short term.

We chose NTX because we know how change in NTX relates to fracture risk reduction with bisphosphonates (20): a 30% decrease in NTX is associated with a 40% reduction in spine fracture and 66% of the vertebral fracture risk reduction at three years is explained by change in NTX. Also, NTX was the marker mostly strongly related to selenium status in our observational study (9).

Secondary endpoints:

Change in serum selenium, selenoprotein P (SePP). Systematic review identified blood selenium and selenoprotein P as robust biomarkers of selenium status, over the range of deficiency to repletion (21).

Change in other bone turnover markers: PINP, osteocalcin, CTX

Change in bone mineral density: lumbar spine and total hip by DXA

Change in muscle function: short physical performance battery (SPPB), hand grip strength. SPPB score is a measure of lower limb strength and balance. It predicts falls, loss of function in activities of daily living, nursing home admission and mortality (22-24).

Change in anti-oxidant activity: glutathione peroxidase activity (a selenium-containing anti-oxidant which is increased in postmenopausal women with osteopenia (25)), hydroperoxides (an oxidative stress marker shown to be associated with bone resorption (26))

Change in inflammatory markers: the pro-resorptive inflammatory cytokine interleukin-6 and highly-sensitive C-reactive protein.

10. ASSESSMENT AND FOLLOW-UP

10.1 Assessment of efficacy/effectiveness

Efficacy measurements will be obtained at baseline, three months and six months.

Blood samples for biochemical measurements will be taken fasted. The approximate maximum blood sample volume at each visit will be 50ml. Urine samples will be obtained as triplicate samples from fasted second morning voids on three days before or including the study visit, and kept refrigerated until the study visit. Equal volume aliquots from the urine samples will be pooled into a single sample by the study team. Samples will be processed according to a sample handling SOP.

Real-time baseline serum selenium will be measured in the Chemical Pathology laboratory, Sheffield Teaching Hospitals.

All other samples will be frozen at -80°C, and analysed in batches at the end of the study.

Urine NTX/Cr will be measured by automated assay (EC Vitros) in the laboratory of the Sheffield Academic Unit of Bone Metabolism or Chemical Pathology laboratory, Sheffield Teaching Hospitals.

Serum selenium at all time points will be measured by X-ray fluorescence spectroscopy (27), selenoprotein P will be measured by immunoassay (28) and glutathione peroxidase by enzyme analysis by [name], Institute for Experimental Endocrinology, Charité - University Medical School Berlin.

Other biochemical markers of bone turnover (serum CTX, PINP and osteocalcin) will be measured by automated assay in the laboratory of the Sheffield Academic Unit of Bone Metabolism.

HsCRP and IL-6 will be measured by the Sheffield Teaching Hospitals Clinical Immunology laboratory.

Hydroperoxidases will be measured using commercially available manual assay kits in the laboratory of the Sheffield Academic Unit of Bone Metabolism.

Grip strength will be assessed using a digital hand dynamometer (Saehan Corporation, Masan, Korea). Three measurements will be taken and the best value used for analysis. Short physical performance battery (SPPB) score will be calculated from a chair stand and narrow walk test (22). *See Appendix 1 – Physical function tests.*

Height and weight will be measured with an electric scale and stadiometer.

Pulse and blood pressure will be measured with an automated sphygmomanometer (Dynamap).

Bone mineral density will be assessed by DXA of the spine and hip (Hologic) at baseline and six months according to standard scanning protocols, by specialist DXA scan technicians in the Sheffield Clinical Research Facility.

Habitual dietary selenium and other nutrient intake (calcium, vitamin D, vitamin E and iodine) will be assessed with seven-day diet diaries. The purpose of the food diaries is to describe participants' habitual dietary intake of selenium and nutrients which influence bone turnover or interact with selenium during the study. The diaries will be analysed using DIETQ (Tinuviel Software, Warrington, UK) by a nutritionist with experience in clinical research.

DNA will be stored for later analysis. There is evidence of glutathione peroxidase genotype influence on selenium action (29). If selenium does reduce bone turnover we can study genotype interactions to better understand its mechanism of action.

10.2 Assessment of safety

Safety assessments for diabetes and thyroid function will be made at screening, baseline, three months and six months. The measurements will be made in real time by Sheffield Teaching Hospitals pathology laboratories. Any parameters outside the reference range will be assessed by the PI or a delegated study doctor for a decision on whether a participant can safely continue, and clinical advice will be given to the participant and GP as required.

Adverse events (including questioning for possible symptoms of selenium toxicity) will be collected from the time of consent, at monthly participant telephone contact throughout the treatment period and by telephone four weeks after the end of treatment.

10.3 Timing of assessments

Baseline and randomisation - within 28 days of screening visit

4W - baseline +28 days (+/-7 days)

8W - baseline +56 days (+/-7 days)

13W - baseline +91 days (window +73 to +94 days)

17W - baseline +119 days (+/-7 days)

21W - baseline +147 days (+/-7 days)

26W - baseline + 182 days (window +172 to +187 days)

30W - 26W + 28 days (+7 days)

See Appendix 2 – Schedule of procedures

11. TRIAL MEDICATION

11.1 Name and description of investigational medicinal product(s)

Selenase 50mcg and Selenase 200mcg (Biosyn, Germany)

Sodium selenite pentahydrate tablets, over-encapsulated.

11.2 Legal status of the drug

The trial is being carried out under a Clinical Trial Authorisation (CTA). The drug is therefore only to be used by the named investigators, for the patients specified in this protocol, and within the trial.

11.3 Summary of Product Characteristics (SmPC)

An IMPD will be submitted to the MHRA who will approve its use in this study. It will be provided by Sharp Clinical Services UK and contain the SmPC for Selenase (translated to English).

The SmPC will be used as the reference safety information (RSI) for assessment of adverse events and classification of expectedness of serious adverse reactions for purposes of SUSAR reporting.

[figure not shown]
The IMPD and SmPC will be stored in the site file. If it is necessary to update the IMPD and SmPC, the new version will be filed in the site file, old versions will be superseded, and the study team will be informed.

11.4 Preparation and labelling of Investigational Medicinal Product

The IMP will be prepared and labelled by Sharp Clinical Services UK. The process will be Annex 13 GMP compliant.

- Selenase 50mcg
 - De-blister Selenase 50mcg tablets.
 - Over-encapsulate one Selenase 50mcg tablet into DBAA el capsules with added Microcrystalline Cellulose
 - Count 93 Selenase 50mcg capsules into child-resistant tamper-evident containers and apply a randomised label to each container.

- Pack two Selenase 50mcg containers, both with the same randomisation number, into cartons and apply the same randomised number label to each carton to produce patient packs and one QA pack
- Selenase 200mcg
 - De-blister Selenase 200mcg tablets.
 - Split one Selenase 200mcg tablet and over-encapsulate both halves into DBAA el capsules with added Microcrystalline Cellulose
 - Count 93 Selenase 200mcg capsules into child-resistant tamper-evident containers and apply a randomised label to each container.
 - Pack two Selenase 200mcg containers, both with the same randomisation number, into cartons and apply the same randomised number label to each carton to produce patient packs and one QA pack
- Placebo
 - Produce DBAA el placebo capsules (filled with appropriate excipient)
 - Count 93 Placebo capsules into child-resistant tamper-evident containers and apply a randomised label to each container.
 - Pack two Placebo containers, both with the same randomisation number, into cartons and apply the same randomised number label to each carton to produce patient packs and one QA pack

- Apply tamper evident seals to patient pack cartons.
- Take one patient pack per batch for QA destructive testing.
- Collate all patient packs together.
- Pack all patient packs into outers for shipping purposes.
- Carry out disintegration testing on the over-encapsulated Selenase tablets.
- Carry out QP final release.

11.5 Drug storage and supply

IMP will be provided by Sharp Clinical Services as above, specifically for use in this trial.

There are two planned manufacturing runs, to allow for possible changes to total participant number after the interim analysis. Further runs may be added if required based on the final sample size, recruitment time and shelf life of IMP.

Each manufacturing run will be delivered to Sheffield Teaching Hospitals pharmacy, under the supervision of the trial pharmacist.

The IMP will be stored at 15 to 25°C in STH pharmacy. Temperature logs will be maintained by STH pharmacy.

The first bottle of 93 tablets will be dispensed at the baseline visit, and the second bottle of 93 tablets at the 13 week visit. Bottles will be labelled with the study identifier (STH19102) and participant randomisation code.

IMP will be dispensed by pharmacy on receipt of a completed study-specific prescription, signed by the PI or delegated registered doctor.

STH pharmacy will retain dispensing records.

Unused or expired IMP at STH will be sent for hazardous waste disposal as per pharmacy SOPs; a record will be kept by pharmacy of what is sent for disposal and reported to the Sponsor if requested.

A 5% excess of patient packs will be manufactured in case a participant loses or damages their medication. If a replacement needs to be supplied, Sharp Clinical Services will advise which spare pack should be used, according to their copy of the randomisation schedule.

Participants will be advised to keep the IMP at room temperature.

